7.2.2 Residual Mass arm

The presence of viable lymphoma cells on biopsy/FNA or absence of lesion progression on medical follow-up will be considered positive for residual malignancy.

8 Statistical Section

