1.3 FDG PET for Response Assessment of Lymphoma at the Conclusion of Therapy

Numerous studies have demonstrated the value of [^{18}F]FDG PET and PET/CT for response assessment of lymphomas at the conclusion of front-line, salvage, or high-dose therapy(2, 18-26). Based on the meta-analysis by Zijlstra et al(18), pooled sensitivity and specificity of FDG-PET for detection of residual disease after completion of first-line therapy were 84% (95% CI, 71% to 92%) and 90% (95% CI, 84% to 94%), respectively, for Hodgkin's lymphoma (HL), and 72% (95% CI, 61% to 82%) and 100% (95% CI, 97% to 100%), respectively, for aggressive Non-Hodgkin's lymphoma (NHL). Accurate information regarding tumor status after treatment of these lymphoma subtypes is critical because these are curable malignancies.

The value of [^{18}F]FDG PET in this setting is its ability to distinguish between viable tumor and necrosis or fibrosis in residual masses. Conventional anatomic imaging modalities frequently are unable to make this distinction because the morphologic features of these tissues are usually indistinguishable (Figure 1 and Figure 2). Moreover, biopsy of a specific site may not be representative of disease activity since areas of necrosis/fibrosis might be interspersed among areas of viable tumor (Figure 3).

[figure not shown]

Figure 1 CT scan of the abdomen prior to chemotherapy demonstrating a large mesenteric mass consistent with biopsy proven lymphoma.

Figure 2 CT scan after chemotherapy demonstrating a decrease in size of the mass but without biopsy, it is impossible to know if there is complete response to treatment.

[figure not shown]

Figure 3 [18F] FDG PET scan after chemotherapy demonstrating the residual mesenteric mass with a central area of viable tumor. Even if a needle biopsy were performed there was a good chance of missing the viable tissue.

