5.1.2 For subjects enrolling in the residual mass arm

Patients enrolled in an NIH Clinical Center lymphoma therapy protocol having a residual mass ≥ 1 cm in longest dimension as measured by the CT component of the PET/CT with FDG uptake greater than that of mediastinal blood pool will undergo an FLT PET/CT within 2 weeks of the post treatment FDG PET/CT study. Patients on other lymphoma therapies from outside institutions, must have a FDG PET/CT positive mass ≥ 1 cm, with uptake greater than that of mediastinal blood pool (81). Participant will undergo a repeat FDG PET/CT scan if the original FDG/PET imaging performed at an outside institution is not of "adequate imaging quality" for subjects enrolling in the residual FDG mass. The patient will undergo an FLT PET/CT within 2

weeks of the FDG PET/CT. Patients will undergo clinically indicated biopsy of the residual mass after FLT PET/CT imaging. Fine needle aspiration (FNA) will be performed when biopsy is not possible. If a biopsy is not medically indicated, then the patient will be followed medically by the Lymphoma Team or by their outside oncologist.

The FLT SUV will be compared with pathological response, with the presence of any viable lymphoma cells on biopsy being considered positive for malignancy. For patients who do not undergo biopsy, the absence of tumor will be assessed by lack of lesion progression on routine medical follow-up. An FLT SUV greater than mediastinal background will be considered positive for malignancy.

5.2 [¹⁸F]FLT PET/CT imaging

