5.3 Pathology (residual mass arm only)

In patients with FDG avid residual masses (uptake greater than mediastinal blood pool) who would routinely undergo biopsy or fine needle aspiration (FNA), the pathology results will be collected and compared with the corresponding FLT SUV. The presence of any viable lymphoma cells will be considered positive for residual malignancy. Biopsy is not medically

indicated in many patients undergoing therapy and therefore, determination of active disease will be based on clinical follow-up in those patients.

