6.2 Concurrent Therapies

No restrictions

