8.1.3 Analysis Plan

For the primary analyses, sensitivity and specificity will be estimated and 95% confidence intervals provided. Subjects with an FLT SUV greater than mediastinal blood pool activity will be considered FLT positive. In the early response arm, subjects with complete response (CR or Cr_u, **Table 6**) as determined by the CHESON revised response criteria will be considered disease negative (all others will be considered disease positive). In the residual mass arm, subjects with any malignant cells on biopsy will be considered disease positive.

For secondary objectives 2a and 2d, empirical ROC curves will be estimated, along with non-parametric AUCs and corresponding 95% confidence intervals. For 2b, we will evaluate the ability of FLT to predict clinical response independent of other known predictors using logistic regression. For aim 2c, we will test for differences using signed-rank tests.

No stratification based on lymphoma histology or treatment is planned due to the small amount of expected variability in treatments available.

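### Section 7.2.2 scores non-progression on follow-up as residual malignancy, the reverse of Section 5.1.2, and the analysis plan has no rule for unbiopsied patients in the residual mass arm

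*Combined protocol and SAP*

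**What the plan says.** Four sections of the combined protocol and SAP define disease status in the residual mass arm.

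- Section 7.2.2, the arm's only response-criteria text: "The presence of viable lymphoma cells on biopsy/FNA or absence of lesion progression on medical follow-up will be considered positive for residual malignancy".
- Section 5.1.2: "For patients who do not undergo biopsy, the absence of tumor will be assessed by lack of lesion progression on routine medical follow-up". It also treats any viable lymphoma cells on biopsy as positive.
- Section 5.3 repeats the biopsy rule, notes that biopsy is not medically "indicated in many patients undergoing therapy", and adds that "determination of active disease will be based on clinical follow-up in those patients". It does not say which follow-up finding means active disease.
- Section 8.1.3: "In the residual mass arm, subjects with any malignant cells on biopsy will be considered disease positive". It has no rule for patients without biopsy. For the early response arm the same section does say how all remaining subjects are classified; for this arm it does not.

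**The concern.** Sections 7.2.2 and 5.1.2 give the same observation, a mass that does not progress, opposite disease labels. Both are complete sentences in current text. The analysis plan, where an analyst would look for the deciding rule, is silent on these patients.

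Objective 1.b is estimated as sensitivity and specificity against this standard. If 7.2.2 is followed, an unbiopsied patient whose mass stays quiet becomes disease positive, and a correct negative FLT scan in that patient becomes a false negative. Section 1.7 reports that 22 of 30 patients are already in this arm and that data have been reviewed. A rule chosen now, with three texts to choose from, could be influenced by the results unless it is settled independently of them.

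**Working it through.** **Inputs from the documents (Section 8.1.4).** 30 patients; 50% with positive pathology, so 30 × 0.50 = 15 positive and 15 negative; anticipated sensitivity about 0.85 and specificity about 0.90; a 50% chance threshold that the lower bounds should exceed.

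**Assumed, because the documents give no figure.** Unbiopsied share u = 10%, 30% or 50%, the same in diseased and non-diseased patients; follow-up separates the true disease states without error.

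**The plan's own figures.** The two-sided exact (Clopper-Pearson) 95% lower limits for 12/15, 13/15 and 14/15 are 0.519, 0.595 and 0.681. Table 8 gives 0.52, 0.60 and 0.68, so it reproduces. The problem lies in the outcome definition and not in the precision table.

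**Effect of 7.2.2 as written.** The section says who is positive but not how an unbiopsied patient who progresses is scored, so both readings are shown.

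*Reading A: progressors remain positive.* The 15u unbiopsied non-progressors join the positives, and 10% of them are FLT positive.

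- Sensitivity = (15 × 0.85 + 15u × 0.10) / (15 + 15u)
- Specificity = 0.90, on 15(1 − u) patients

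*Reading B: progressors become negative.* The two unbiopsied groups change places.

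- Sensitivity = 0.85(1 − u) + 0.10u
- Specificity = 0.90(1 − u) + 0.15u

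| u | A: sensitivity | A: specificity (expected negatives) | B: sensitivity | B: specificity |
|---|---|---|---|---|
| 10% | 12.9/16.5 = 0.78 | 0.90 (13.5) | 0.775 | 0.825 |
| 30% | 13.2/19.5 = 0.68 | 0.90 (10.5) | 0.625 | 0.675 |
| 50% | 13.5/22.5 = 0.60 | 0.90 (7.5) | 0.475 | 0.525 |

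Under the 5.1.2 direction, with the same assumptions, the values stay at 0.85 and 0.90 on 15 and 15.

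**A whole-number case.** Suppose the true results are 13/15 for sensitivity and 14/15 for specificity, and some FLT-negative non-progressors are unbiopsied and counted as malignant.

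- Three such patients: sensitivity 13/18 = 0.72, exact lower bound 0.465 (0.47), against 0.60 for 13/15. Specificity 11/12, lower bound 0.615.
- Five such patients: sensitivity 13/20 = 0.65, exact 95% CI 0.41 to 0.85. Specificity 9/10, lower bound 0.56, against 0.68 for 14/15.

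Three misclassified patients are enough to take the sensitivity lower bound below 50%.

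**The case against.** The strongest reply is that this is a drafting slip with limited reach. Section 5.1.2 states the sensible direction in a full sentence, 8.1.3 does not repeat the reversed wording, and a careful analyst would probably follow 5.1.2. The documents do not show that the analysis would be run in reverse. That stands, and it limits the claim to a contradiction that must be reconciled. It does not remove the point, because 7.2.2 is the arm's named response criterion and 8.1.3 offers nothing to override it.

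Three stronger readings are tempting, and the documents do not support them.

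- *The reference standard is inverted for the whole arm.* The rule that viable cells on biopsy mean disease agrees in 5.1.2, 5.3, 7.2.2 and 8.1.3. Sections 5.1.2 and 5.3 send only patients without biopsy to follow-up, so only they are affected.
- *A negative needle biopsy is final, so missed tumor is scored as absent.* A reader might infer this from a figure caption in Section 1.3, "Even if a needle biopsy were performed there was a good chance of missing the viable tissue", and the body text there makes a similar general remark. But no section says a negative biopsy is final. Section 7.2.2 joins its two criteria with an or and does not confine follow-up to the unbiopsied. Any resulting loss of specificity would also need a miss rate that the documents do not give.
- *Treated tumor counts as no tumor, because Section 6.2 says "No restrictions".* That line concerns therapy concurrent with the imaging study, and Section 6.6 ends participation when FLT imaging is complete. It does not govern treatment during later follow-up. What remains is a gap: 5.1.2 sets no follow-up duration and no condition on intervening treatment.

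**Conclusion.** The contradiction is real and sits in the reference standard for a primary objective. It affects only patients classified by follow-up, a group that Section 5.3 calls many without giving a number. Over an assumed 10% to 50% unbiopsied, apparent sensitivity falls from 0.85 to between 0.78 and 0.60 with specificity held at 0.90, or to between 0.78/0.83 and 0.48/0.53 if progressors are also reversed. These figures rest on the protocol's anticipated accuracy and 15/15 split, an equal unbiopsied share in both groups and error-free follow-up. They show what following 7.2.2 would do and do not predict the result. The sample size does not need to change because of this wording.

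**What to change.** Reconcile 7.2.2 with 5.1.2 and carry one rule into 8.1.3:

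- Disease positive: viable lymphoma cells on biopsy or FNA, or lesion progression on follow-up.
- Disease negative: no viable cells on biopsy or FNA or, if unbiopsied, no lesion progression on follow-up.

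State that the positive rule is applied first, so that a biopsy-negative patient who later progresses cannot fall under both definitions. Settle the text before the final analysis and without reference to FLT results, given the 22 of 30 already enrolled and the data review in Section 1.7. Report a biopsy-only estimate as a sensitivity analysis.

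A prespecified minimum follow-up and a rule for intervening therapy would make the standard more complete, but they go beyond correcting the error and are for the sponsor to decide.

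The cost is a short amendment and a little extra analysis. Sections 6.6 and 7.1 already allow follow-up clinical data from referring physicians.

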8.1.4 Sample size

We plan to enroll 40 participants in the first arm and 30 participants in the residual tumor arm.

In the first arm, we assume that patients enrolled in this trial come from a randomized trial of DA-EPOCH-R vs. R-CHOP. With DA-EPOCH-R treatment, the expected response rate is 74%(92), while with R-CHOP it is 50%. (21). If we assume half of the patients enrolled in this trial will receive DA-EPOCH-R and the other half will receive R-CHOP, the average response rate is 62%, which will provide about 25 responders, who will contribute to estimates of sensitivity. About 15 patients will be non-responders and will contribute to estimates of specificity. The lower bounds for sensitivity are given in **Table 7**. Lower bounds for specificity are given in **Table 8**.

For the second primary objective, we assume that the 50% of patients with FDG positive residual disease will have positive pathology.(93) This provides 15 positives and 15 negatives. **Table 8** provides lower bounds for confidence intervals for sensitivity and specificity for this objective.

The following table provides expected lower bounds for 95% confidence intervals given observed values of sensitivity and specificity for a sample size of 15. We anticipate sensitivity and specificity to be about 85% and 90%, respectively. Hence, the sample size will provide lower bounds above the chance threshold of 50%.

Table 7

Sensitivity (n=25)	Expected lower bound of exact 95% CI
20/25(=.80)	0.59
21/25(=.84)	0.64
22/25(=.88)	0.69

Table 8

Sensitivity/Specificity (n=15)	Expected lower bound of exact 95% CI
12/15 (=0.8)	0.52
13/15 (=0.87)	0.60
14/15 (=0.93)	0.68

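### Section 7.2.2 scores a non-progressing, unbiopsied residual mass as malignant, contradicting section 5.1.2; section 8.1.3 does not settle which rule applies to primary objective 1.b

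*Combined protocol and SAP*

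**What the plan says.** Four sections bear on how a residual-mass patient is classed as diseased or not.

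- Section 7.2.2, under the response criteria: "The presence of viable lymphoma cells on biopsy/FNA or absence of lesion progression on medical follow-up will be considered positive for residual malignancy".
- Section 5.1.2, in the trial design: "For patients who do not undergo biopsy, the absence of tumor will be assessed by lack of lesion progression on routine medical follow-up".
- Section 5.3 says biopsy is not medically "indicated in many patients undergoing therapy and therefore, determination of active disease will be based on clinical follow-up in those patients". It does not say which follow-up finding means active disease.
- Section 8.1.3, the analysis plan: "In the residual mass arm, subjects with any malignant cells on biopsy will be considered disease positive". Patients without a biopsy are not mentioned.

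The index test rule, also in 8.1.3, is "Subjects with an FLT SUV greater than mediastinal blood pool activity will be considered FLT positive". Sensitivity and specificity with 95% confidence intervals are the primary analyses. Section 8.1.4 plans 30 patients in this arm and states "we assume that the 50% of patients with FDG positive residual disease will have positive pathology", giving 15 positives and 15 negatives. It expects sensitivity of about 85% and specificity of about 90%, and concludes that the lower confidence bounds will exceed 50%.

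**The concern.** Sections 7.2.2 and 5.1.2 give opposite disease labels to the same patient: one with no biopsy and no progression. Section 7.2.2 gives no rule for calling a patient negative. An unbiopsied patient whose lesion does progress meets neither of its two positive criteria.

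The label is the reference standard for primary objective 1.b, so a wrong label changes the 2x2 table directly. If 7.2.2 were applied as written, a stable, unbiopsied, FLT-negative mass would change from a true negative to a false negative. A stable, unbiopsied, FLT-positive mass would change from a false positive to a true positive. Because FLT is expected to be negative in about 90% of non-diseased patients, the first movement would dominate and estimated sensitivity would fall. The disease-negative group, on which specificity rests, would also shrink.

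Follow-up is a planned route to the label. Section 5.1.2 leaves it to the study's lymphoma team or to an outside oncologist, so the rule needs to read the same way to more than one person.

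**Working it through.** **Inputs.** From 8.1.4: 30 patients, 50% with positive pathology, hence 30 × 0.50 = 15 diseased and 15 non-diseased; sensitivity 0.85; specificity 0.90; threshold 0.50 for the lower bound. Assumed, because the documents give no figure: an unbiopsied share u, equal in diseased and non-diseased patients, shown at 20%, 30% and 50%. Also assumed: follow-up reflects true status, so diseased masses progress and non-diseased ones do not.

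**The plan's own figures.** The Clopper-Pearson two-sided 95% lower limit is the 2.5% quantile of a Beta(x, n − x + 1) distribution. For n = 15 it gives 0.519, 0.595 and 0.681 at 12, 13 and 14 successes. Table 8 states 0.52, 0.60 and 0.68, so the table reproduces.

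**Scenario 1: only non-progressors are mislabelled.** This is the error that 7.2.2 states directly. Progressors are kept as positive. The 15u unbiopsied non-diseased patients join the positive group, and 10% of them are FLT-positive:

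- Sensitivity = (15 × 0.85 + 15u × 0.10) / (15 + 15u) = (0.85 + 0.10u) / (1 + u)
- Disease-negative group = 15(1 − u); expected specificity stays at 0.90
- Expected true negatives turned into false negatives = 15u × 0.90

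**Scenario 2: progressors are also scored negative.** This needs the further step of reading a patient not listed as positive as negative:

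- Sensitivity = 0.85(1 − u) + 0.10u
- Specificity = 0.90(1 − u) + 0.15u

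| u | Scenario 1 sensitivity | Scenario 1 negative group | Scenario 2 sensitivity / specificity |
|---|---|---|---|
| 20% | 0.87/1.2 = 0.73 | 12 | 0.70 / 0.75 |
| 30% | 0.88/1.3 = 0.68 | 10.5 | 0.63 / 0.68 |
| 50% | 0.90/1.5 = 0.60 | 7.5 | 0.48 / 0.53 |

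In scenario 1 the expected number of true negatives turned into false negatives is 2.7 at u = 20% and 6.8 at u = 50%.

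**Whole-patient example.** Start from two rows of Table 8: sensitivity 13/15 (lower bound 0.60) and specificity 14/15 (lower bound 0.68). Re-score three FLT-negative, unbiopsied, non-progressing patients as diseased. Sensitivity becomes 13/(15 + 3) = 13/18 = 0.72, with exact lower bound 0.465. Specificity becomes 11/12 = 0.92, with lower bound 0.615. With five such patients, sensitivity is 13/20 = 0.65, with lower bound 0.41. Three patients are therefore enough to take the sensitivity bound below 0.50.

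**With 7.2.2 aligned to 5.1.2** the 15/15 table and the Table 8 bounds stand, and the sample size does not change.

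**The case against.** The strongest reply is that this is a wording error that no careful analyst would apply. Section 5.1.2 states the intended direction plainly. The end of section 1.6 and section 5.3 both speak of determining active disease by biopsy or follow-up, and on an ordinary reading a stable mass is not evidence of active disease. The analysis rule in 8.1.3 refers to malignant cells on biopsy and does not use absence of progression as a positive criterion. The sample size is likewise framed in terms of pathology.

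Much of this stands. It makes a slip the likely explanation and makes the harm conditional on 7.2.2 being followed literally. It does not remove the conflict, because 8.1.3 is silent on unbiopsied patients. Someone looking for an explicit positive criterion based on follow-up finds one only in 7.2.2, where it points the wrong way.

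Three stronger readings are tempting, and the documents do not support them.

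- A reader might infer that every unbiopsied patient's label is reversed. Section 7.2.2 states only what is positive. It mislabels non-progressors and leaves progressors without a rule. Scenario 2 needs that silence to be read as negative, so it is the more extreme case and not the main result.
- A reader might infer that the reversed rule governs the primary analysis. No section says that 7.2.2 overrides 8.1.3.
- A reader might infer that recorded outcomes are already wrong. The data elements listed in 7.1 include no residual-mass outcome label. The interim remark in 1.7, that FLT seems to separate viable from inflammatory masses better than FDG, would be hard to square with reversed labels, although that is only an inference.

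The size of the effect is also open to challenge. The wording in 5.3 gives no proportion for this arm, and biopsy follows clinical indication, so the unbiopsied share may differ between diseased and non-diseased patients.

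**Conclusion.** The contradiction is real, lies in current text, and must be corrected before analysis because it concerns the reference standard for a primary objective. It would do harm only if 7.2.2 were applied as written.

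In that case, mislabelling non-progressors alone would lower expected sensitivity from 0.85 to between 0.73 and 0.60 over unbiopsied shares of 20% to 50%, and would cut the disease-negative group from 15 to between 12 and 7.5. The plan's statement that lower bounds will exceed 50% could fail for sensitivity with as few as three re-scored patients. Scoring progressors as negative as well would give sensitivity/specificity between 0.70/0.75 and 0.48/0.53.

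These figures rest on the plan's own 15/15 split and accuracy, on an assumed unbiopsied share equal in both groups, and on follow-up that reflects true status. No section defines progression or a minimum follow-up for this arm, so the last assumption cannot be checked from the documents. The Table 8 arithmetic is correct and is not in question.

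**What to change.** Rewrite 7.2.2 to agree with 5.1.2. A patient is positive for residual malignancy if biopsy or FNA shows viable lymphoma cells or, where neither was done, if the lesion progresses on follow-up. A patient with neither biopsy nor FNA and no progression is negative.

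Put the same rule in 8.1.3. Correcting 7.2.2 alone would leave the primary-analysis text without a rule for unbiopsied patients.

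Section 1.7 reports 22 of 30 patients accrued to this arm. Check any outcome labels already assigned to those 22 against the corrected rule.

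The cost is a short amendment to two sections and a review of existing labels. It needs no new data, no change in sample size and no change in patient care.

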8.1 Objectives

8.1.1 Primary Objectives

- 1.a. To estimate the diagnostic accuracy of FLT PET/CT as an early indicator of complete response to therapy in B and T cell lymphoma.
- 1.b To estimate the diagnostic accuracy of FLT PET/CT in the evaluation of residual masses after therapy.

